3.4.4.2 Analyses of secondary efficacy endpoints

Method for controlling the overall type-I error rate when testing the main secondary efficacy endpoints is described in Section 3.4.4.3.

Secondary endpoints will be analyzed using the same statistical methodology as for the primary endpoint.

3.4.4.3 Multiplicity issues

In order to handle multiple main secondary endpoints, the overall type-I error will be controlled by the use of a sequential inferential approach. Statistical significance of the primary endpoint is required before drawing inferential conclusions about first main secondary endpoint (at the 0.0001 1-sided alpha level at the second interim analysis or at the 0.0249 1-sided alpha level at the final analysis). Inferential conclusions about successive main secondary parameters require statistical significance of the prior one. The order of tests is detailed in Section 3.1.3.2.1.

This fixed hierarchical approach will ensure a strong control of the overall type-I error rate at the required 1-sided level (0.0001 for the second interim analysis and 0.0249 at the final analysis).

No further adjustments will be made for other secondary endpoints for which p-values will be provided for descriptive purpose only.

3.4.4.4 Additional efficacy analyses

Additional efficacy analyses, endorsed by the steering committee, may be defined in an exploratory SAP, before the unblinding of the treatment code. In particular the relationship between lipid lowering effects and the outcome of cardiovascular efficacy endpoints will be assessed.

Additional analyses will be performed to explore if the randomized treatment effects on cardiovascular efficacy endpoints are statistically different before and after a specified timepoint (e.g. 0-1 year vs. >1 year). These analyses will be performed with Cox proportional hazard models. Specifically, for a given endpoint, the model fit that allows the treatment HR to vary before and after the specified timepoint (with adjustment for region) will be compared to the corresponding model where the treatment HR is not allowed to vary over time.

3.4.5 Analyses of safety data

The summary of safety results will be presented by treatment group.

General common rules

All safety analyses will be performed on the safety population as defined in Section 3.3.2, unless otherwise specified, using the following common rules:

- Safety data in patients who do not belong to the safety population (ie, exposed but not randomized) will be listed separately;
- The baseline value is defined as the last available value before first double-blind IMP injection, except otherwise specified;
- The potentially clinically significant abnormality (PCSA) values are defined as abnormal values considered medically important by the Sponsor according to predefined criteria/thresholds based on literature review and defined by the Sponsor for clinical laboratory tests, vital signs, and ECG (see Appendix A). In case the PCSA threshold is within the normal laboratory ranges, the analysis will be done using "<LLN" or ">ULN" threshold instead of "<PCSA threshold" or ">PCSA threshold" respectively. Of note, for HbA_{1c}, usual PCSA criteria will not be applied as specific analysis for the incidence of diabetes during the TEAE period will be provided, combining information from adverse event, laboratory parameters, and antidiabetic medications (see detail in Section 3.4.5.3).
- PCSA criteria will determine which patients had at least 1 PCSA during the TEAE period, taking into account all evaluations performed during this period, including nonscheduled, local or repeated evaluations.
- The treatment-emergent PCSA denominator by group for a given parameter will be based on the number of patients assessed for that given parameter in the TEAE period by treatment group on the safety population.
- All measurements, scheduled or unscheduled, fasting or not fasting, will be assigned to analysis windows defined in Section 3.5.4 Table 8.
- For quantitative safety parameters based on central laboratory/reading measurements, descriptive statistics will be used to summarize results and change from baseline values by visit (using analysis windows defined in Section 3.5.4 Table 8) and treatment group. Summaries will include the last on-treatment value and the worst on-treatment value.
- The worst value is defined as the nadir and/or the peak value during the treatment period according to the direction (minimum or maximum) of the abnormality as defined in the PCSA list.
- For exploratory purpose, safety analyses could also be provided according to up-titration status, ie, according to whether the patients remained on the 75 mg dose or whether they were up-titrated to 150 mg. These analyses will be exploratory and descriptive (no formal comparison per dose) as it is expected that there could be inherent differences in the baseline characteristics between those patients titrating to 150 mg and those remaining on 75 mg. In order to reduce the bias of this analysis, the period before the up-titration for patients up-titrated and the period before the first up-titration time point (ie, Month 2) for patients not up-titrated will not be included in the analysis since only the dose 75 mg is proposed for this time period and consequently the early events can only be attributed to

this dose. Therefore the descriptive analysis per dose will include any safety events occurring from the first injection post up-titration time point IVRS/IWRS transaction to the end of the TEAE period or to 70 days after down-titration to 75 mg (if any), whichever comes first. Event-rate per patient-year will also be provided after up-titration time point to take into account variable duration of exposure.

• Analyses performed according to diabetes mellitus status at baseline will be done using the definition provided in Section 3.1.1.

3.4.5.1 Analyses of adverse events

Generalities

The primary focus of adverse event reporting will be on TEAEs. Pre- and post-treatment adverse events will be described separately.

If an adverse event date/time of onset (occurrence, worsening, or becoming serious) is incomplete, an imputation algorithm will be used to classify the adverse event as pre-treatment, treatment-emergent, or post-treatment. The algorithm for imputing date/time of onset will be conservative and will classify an adverse event as treatment emergent unless there is definitive information to determine it is pre-treatment or post-treatment. Details on classification of adverse events with missing or partial onset dates are provided in Section 3.5.3.

Adverse event incidence tables will present by SOC, HLGT, HLT, and PT, sorted in alphabetical order for each treatment group, the number (n) and percentage (%) of patients experiencing an adverse event. Multiple occurrences of the same event in the same patient will be counted only once in the tables within a treatment phase. The denominator for computation of percentages is the safety population within each treatment group.

Sorting within tables should ensure the same presentation for the set of all adverse events within the observation period (pre-treatment, treatment-emergent, and post-treatment). For that purpose, the table of all TEAEs presented by SOC and PT sorted by the internationally agreed SOC order and decreasing frequency of PTs within SOCs will define the presentation order for all other tables unless otherwise specified. Sorting will be based on results for the alirocumab group.

As recommended by the safety planning, evaluation, and reporting team (SPERT, [6]) the analysis of all TEAEs will be split into 3 tiers for signal detection and analysis of adverse events.

- Tier 1: TEAEs with pre-specified detailed analysis: TEAEs for which hypothesis and comprehensive analytical approach are prospectively defined.
- Tier 2: signal detection among common TEAE: (not prespecified).
- Tier 3: descriptive analysis of infrequent TEAEs: TEAEs which are infrequent. This could include some AESI predefined in the protocol (eg, pregnancy, hemolytic anemia) to ensure close monitoring but which are expected to be so rare that statistical analysis is not meaningful. For those events, medical judgment should prevail.

Prospective analysis for Tier 1 events

Tier 1 events will include the AESIs and grouping of adverse events as defined in Section 3.1.4.1. Some of these events may be analyzed as Tier 3 in case their occurrence is infrequent. For each selected Tier 1 event, comprehensive analytic approach will be conducted, as described below, in order to evaluate whether the incidence is higher in the alirocumab group versus the placebo group.

Descriptive summaries of Tier 1 events

The number (%) of patients with an event in the TEAE period will be summarized in each treatment group: 95% CIs of the incidence rate (%) will be provided (CI calculated using the mid-p method) for each Tier 1 grouping of terms. The event rate per 100 patient-years (the number of patients with an event in question divided by total 100 patient-years), as well as 95% CI will be also provided. For a patient with an event, patient year is censored at time of first event; for patient without event, it corresponds to the length of the TEAE period. If the event is defined as a grouping of terms, the table will be presented by SMQ/CMQ and PT (when selection is based on SMQ/CMQ) and by PT (when selection is based on the e-CRF tick box or HLGT/HLT), showing the number (%) of each PT included in the grouping of terms. The summaries will be sorted by decreasing incidence of PT within each SMQ/CMQ (in the alirocumab group). In addition, above description will be provided according to diabetes mellitus status at baseline for the diabetes mellitus or diabetic complications grouping.

An overview of each Tier 1 TEAE will be also provided in each treatment group: number (%) of TEAE, of treatment-emergent SAE, of TEAE leading to death and of TEAE leading to permanent treatment discontinuation. In addition, a summary of the following characteristics at grouping level will be provided: the severity grade (mild, moderate, severe), the outcome (Recovered/Resolved, Recovering/Resolving, Unknown, Recovered/Resolved with sequelae, Stabilized, Not recovered/Not Resolved, Fatal), the seriousness, the outcome status of Tier 1 TEAE leading to premature treatment discontinuation. In addition, summary by SMQ/CMQ and PT will be provided for serious TEAEs and TEAEs leading to permanent treatment discontinuation.

Time to liver-related treatment discontinuation and time to liver death may also be provided using hepatic disorder SMQ.

Additional statistical analyses for Tier 1

In order to compare treatment groups, the hazard ratio (HR) will be provided together with the corresponding 95% CI. Hazard ratio will be calculated using a Cox model. Patient without any event will be censored at the end of the TEAE period.

Kaplan-Meier curves for time from first dose of double-blind IMP to the first occurrence of Tier 1 TEAE will be provided for each Tier 1 (grouping of terms). Patient without any event will be censored at the end of the TEAE period.

In addition, HR and Kaplan-Meier curves and estimates will be provided according to diabetes mellitus status at baseline for the diabetes mellitus or diabetic complications grouping.

To assess the homogeneity of the treatment effect across age groups (<65 years versus \geq 65 years, and <75 years versus \geq 75 years), the treatment-by-age interaction will be tested in a Cox model including the age factor term and the treatment-by-age interaction term. Hazard ratio and the corresponding 95% CI within each age subgroup (calculated using a Cox model), as well as the significance level of the treatment-by-age interaction term will be also provided for descriptive purpose.

Additional summaries for local injection site reaction

The following description of local injection site reaction will be tabulated:

- Number of local injection site reaction per patient: 1, >1;
- Mean duration;
- Number of events divided by the number of double-blind IMP injections received;
- Time from first double-blind IMP injection to first local injection site reaction;
- Number of double-blind IMP injections received up to the first event;
- Intensity of the event (mild, moderate, severe);
- Description of the highest intensity of each symptom recorded in the specific e-CRF page.

Analysis of all "common" TEAE(s) - Tier 2 events

"Common" events are defined as those for which there are more (>) than n patients with an event overall in the safety population. This threshold will be defined as the number of patients with events (n) observed overall (whatever the treatment group) for which the extreme case scenario (n for alirocumab versus 0 for the placebo) doesn't allow the p-value to be less than 0.05.

All common TEAEs (by HLT and PT), showing the number (%) of TEAE, the event rate per 100 patient-years, HR (estimated using a Cox model) with the corresponding 95% CI, sorted by decreasing incidence rate in alirocumab group in one table, and by decreasing HR in the another table, will be analyzed.

If any clinically significant signal is detected and need further characterization, additional analyses similar to Tier 1 analyses, will be provided.

Descriptive analysis of infrequent adverse events – Tier 3 events

All infrequent TEAEs (Tier 3) will be reported with descriptive statistics (n, %) and event rate per 100 patient year, without comparative statistics since with so rare event statistical comparisons are not meaningful and medical judgment should prevail.

Analysis of all treatment-emergent adverse events

The following TEAE summaries, including all TEAEs (common or not, Tier 1 or not) will be generated for the safety population.

- Overview of TEAEs, summarizing number (%) of patients with any:
 - TEAE;
 - Serious TEAE;
 - TEAE leading to death;
 - TEAE leading to permanent treatment discontinuation.
- All TEAEs by primary SOC, HLGT, HLT, and PT, sorted by the SOC internationally agreed order. The other levels (HLGT, HLT, PT) will be presented in alphabetical order;
- All TEAEs regardless of relationship and related to IMP by primary SOC, HLGT, HLT, and PT, sorted by the internationally agreed SOC order. The other levels (HLGT, HLT, PT) will be presented in alphabetical order;
- All TEAEs regardless of relationship and related to statin/other lipid lowering drug by primary SOC, HLGT, HLT, and PT, sorted by the internationally agreed SOC order. The other levels (HLGT, HLT, PT) will be presented in alphabetical order;
- All TEAEs by primary SOC and PT, sorted by the internationally agreed SOC order and by decreasing incidence of PTs within each SOC (in the alirocumab group). This sorting order will be applied to all other tables by SOC and PT of TEAEs, unless otherwise specified. The event rate per 100 patient-years (the number of patients with an event in question divided by total patient-years) will be provided for all TEAEs by SOC and PT. For a patient with event, patient-year is censored at time of first event; for patient without event, it corresponds to length of TEAE period;
- All TEAEs that occurred with HLT and PT incidence ≥2% in alirocumab group and at incidence at least 0.5% higher in alirocumab than placebo, by primary SOC, HLT, and PT;
- All TEAEs that occurred with incidence ≥5% in any treatment group, by primary SOC and PT, with event rate per 100 patient-years;
- All TEAEs by maximal severity (ie, mild, moderate, or severe), presented by primary SOC and PT.

Subgroup of patients with 2 consecutive LDL-C <25 mg/dL (<0.65 mmol/L)

A 2-step approach will be used to analyze the safety in relation to low LDL-C.

The first step will screen events for potential signal using 2 approaches. The first approach will be a direct comparison of patients with 2 consecutive LDL-C <25 mg/dL versus \geq 25 mg/dL (ie, patients without 2 consecutive LDL-C <25 mg/dL) within the alirocumab treatment group. Since these 2 groups are based on post-randomization data with a potential for bias, a second approach will compare the alirocumab effect versus placebo according to categories based on baseline LDL-C. The frequency of patients with 2 consecutive LDL-C <25 mg/dL is expected to be the largest in the category with the lowest baseline LDL-C and be lower and lower in the categories with higher baseline LDL-C. Therefore, an event induced by low LDL-C should be associated with a higher alirocumab effect versus placebo (ie, higher HR) in the first baseline LDL-C category(ies) than in the subsequent categories. Details of these 2 approaches are provided below.

The second step will consist in the comparison of patients with 2 consecutive LDL-C <25 mg/dL versus \geq 25 mg/dL within the alirocumab group for the events detected in the first step, as well as for pre-specified events.

Similar analyses will be provided considering 15 mg/dL (0.39 mmol/L) as threshold instead of 25 mg/dL.

First step

First screening approach

TEAE summary by primary SOC, HLGT, HLT, and PT as well as groupings of events (ie, cataract, neurological events, neurocognitive disorders and "new onset of diabetes" [see Section 3.4.5.3 for the definition]) will be provided on the safety population in the groups below:

- Placebo group
- Alirocumab group
- Alirocumab LDL-C \geq 25 mg/dL (ie, alirocumab patients without 2 consecutive LDL-C <25 mg/dL)
- Alirocumab patients with 2 consecutive LDL-C <25 mg/dL

For patients with 2 consecutive LDL-C <25 mg/dL, analyses will be done on the period starting from the first of the 2 consecutive LDL-C lower than 25 mg/dL to the upper limit of the TEAE period excepted for patients down-titrated from 150 mg to 75 mg for whom the analysis period will end at the date of last injection of 150 mg +70 days (as patients down-titrated from 150 mg to 75 mg are likely to come back above 25 mg/dL).

The time to the first TEAE/event will be compared for patients with 2 consecutive LDL-C <25 mg/dL versus $\geq 25 \text{ mg/dL}$, within the alirocumab group, using a Cox model, including the covariate for 2 consecutive LDL C <25 mg/dL (Yes/No). Hazard ratio (and 95% CI) from this model will be provided. The event rate per 100 patient-years (the number of patients with an event in question divided by total 100 patient-years) will also be provided.

Second screening approach

TEAE summary by primary SOC, HLGT, HLT, and PT as well as groupings of events (ie, cataract, neurological events, neurocognitive disorders and "new onset of diabetes" will be provided on the safety population according to baseline LDL-C categories (eg, <70, ≥70 to <90, ≥90 to <110, ≥110 mg/dL).

Hazard ratio (and 95% CI) for alirocumab effect versus placebo within each baseline LDL-C subgroup will be provided using a Cox model with baseline LDL-C (in categories), treatment group and the treatment-by-baseline LDL-C interaction term.

To assess the impact of baseline LDL-C on hazard ratio, a Cox model including the baseline LDL-C (as continuous factor), treatment group and treatment-by-baseline LDL-C interaction term will be used. The p-value from the interaction term will be provided for descriptive purpose to evaluate if there is a potential relationship between baseline LDL-C and hazard ratio.

Second step

For each pre-specified event (cataract, neurological events, neurocognitive disorders, new onset of diabetes) as well as for each event with a potential signal detected in the first step, the time to the first TEAE/event will be compared for patients with 2 consecutive LDL-C <25 mg/dL versus \geq 25 mg/dL, within the alirocumab group, using a Cox model, including the covariate for 2 consecutive LDL-C <25 mg/dL (Yes/No) and prognostic factors of the event analyzed. Adjusted HR (and 95% CI) from this model will be provided.

The list of prognostic factors will be established based on the literature and on study data (as applicable).

Subgroups of patients with treatment-emergent ADA positive response

All TEAEs by primary SOC, HLGT, HLT, and PT as well as local injection site reactions will be described in the alirocumab group according to the following ADA parameters:

- Treatment-emergent ADA positive response (yes/no)
- Persistent/transient/indeterminate treatment-emergent ADA positive response.

Analysis of all treatment-emergent serious adverse event(s)

- All treatment-emergent SAEs by primary SOC, HLGT, HLT, and PT, sorted by the internationally agreed SOC order. The other levels (HLGT, HLT, PT) will be presented in alphabetical order;
- All treatment-emergent SAEs regardless of relationship and related to IMP, by primary SOC, HLGT, HLT, and PT, sorted by the internationally agreed SOC order. The other levels (HLGT, HLT, PT) will be presented in alphabetical order;
- All treatment-emergent SAEs by primary SOC and PT.

Analysis of all treatment-emergent adverse event(s) leading to permanent treatment discontinuation

- All treatment-emergent adverse events leading to treatment discontinuation, by primary SOC, HLGT, HLT, and PT, sorted by the internationally agreed SOC order. The other levels (HLGT, HLT, PT) will be presented in alphabetical order;
- All TEAEs leading to treatment discontinuation by primary SOC and PT.

Analysis of pre-treatment and post-treatment adverse events

- All pre-treatment adverse events by primary SOC and PT sorted by the internationally agreed SOC order and decreasing incidence of PTs within each SOC;
- All pre-treatment adverse events leading to treatment discontinuation (if any) by primary SOC and PT, sorted by the internationally agreed SOC order and decreasing incidence of PTs within each SOC;
- All post-treatment adverse events by primary SOC and PT, sorted by the internationally agreed SOC order and decreasing incidence of PTs within each SOC;
- All post-treatment SAEs by primary SOC and PT, sorted by the internationally agreed SOC order and decreasing incidence of PTs within each SOC.

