- Neurologic events selected using a CMQ, based on SMQs "demyelination" (broad and narrow), "peripheral neuropathy" (broad and narrow), and "Guillain-Barre syndrome" (broad and narrow) excluding the following preferred terms "acute respiratory distress syndrome", "asthenia", "respiratory arrest" and "respiratory failure" and including selected PTs from SMQ "optic nerve disorders" (see Appendix B Table 13 for the list of terms)
- Neurocognitive events:
 - Selected using a CMQ, based on the following 5 HLGTs: "deliria (including confusion)", "cognitive and attention disorders and disturbances", "dementia and amnestic conditions", "disturbances in thinking and perception", and "mental impairment disorders"
 - A second grouping of terms for neurocognitive events was defined based on Regulatory Agency request (see Appendix B Table 14 for the list of terms)
- Overdose of IMP (symptomatic or asymptomatic), selected using appropriate MedDRA codes and the tick box "Overdose with IMP" in the adverse event complementary e-CRF form
- Pregnancy (including partner of a randomized male subject) selected using appropriate MedDRA codes

In addition the additional grouping of events will be provided:

- Hepatic disorder events using SMQ "Hepatic disorder"
- Diabetes mellitus or diabetic complications using HLGT "diabetes complications" (including PTs pertaining to the secondary SOC included in the HLGT), HLT "diabetes mellitus", and HLT "carbohydrate tolerance analyses (incl diabetes)" excluding PTs "blood glucose decreased" and "Glycosylated haemoglobin decreased" and including the PTs "hyperglycaemia", "Hyperglycaemic unconsciousness" and "Hyperglycaemic seizure" from the HLT "Hyperglyceamic conditions NEC"
- New onset of diabetes (in the subgroup of patients not having diabetes at baseline) (see definition in Section 3.4.5.3)
- Cataract using HLT "Cataract conditions"

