3.4.5.3 Analyses of laboratory variables

Descriptive statistics over time

The summary statistics (including number, mean, median, Q1, Q3 standard deviation, minimum, and maximum) of all laboratory variables (central laboratory values and changes from baseline) will be calculated for each visit or study assessment (baseline, each post-baseline time point, last on-treatment and worst on-treatment value) by treatment group during the treatment period.

For glucose, this summary will be also provided according to the diabetes status at baseline. Only fasting samples will be summarized.

In addition, for some parameters of interest, mean changes from baseline with the corresponding standard error could be plotted over time in each treatment group.

Potentially clinically significant abnormalities

The incidence of PCSAs (list provided in Appendix A) as well as ALT increase as defined as AESI and hemoglobin decrease from baseline ≥ 15 g/L at any time during the TEAE period will be summarized by biological function and treatment group whatever the baseline level and/or according to the following baseline status categories:

- Normal/missing;
- Abnormal according to PCSA criterion or criteria.

For glucose, this summary will also be provided according to the diabetes status at baseline. Only fasting samples will be summarized.

For parameters for which no PCSA criteria are defined, similar table(s) using the normal range will be provided.

PCSA summaries will also be provided in patients from alirocumab group with 2 consecutive LDL-C <25 mg/dL in case a signal detected in the adverse events analyses (see Section 3.4.5.1) warrants further investigations. Only PCSA occurring after the first occurrence of LDL-C <25 mg/dL will be considered (see Section 3.4.5.1, sub-section "Subgroup of patients with two consecutive LDL-C <25 mg/dL (<0.65 mmol/L)" for the definition of the analysis period).

Analysis of new onset of diabetes (NOD)

The incidence of new onset of diabetes during the TEAE period will be analyzed in the subgroup of patients not having diabetes at baseline as well as in the subgroups of patients with pre-diabetes and normal glycemic at baseline (see Section 3.1.1). New onset diabetes will be defined as follows, combining information from adverse events, medication, and laboratory parameters:

- Type 1 or 2 diabetes TEAE (CMQ "Type 1 or type 2 diabetes", Table 11).

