- And/or anti-diabetic medication initiated during the TEA E period with a confirmed diagnosis per the external diabetes experts *.

* Patients classified as NOD based only on the use of anti-diabetic medication during the TEAE period will be reviewed in a blinded manner by external experts in diabetology. If the diabetic mellitus status is not confirmed, the patients will not be classified as NOD.

- And/or at least 2 HbA_{1c} \geq 6.5% during the TEAE period
 - For patients with a single measurement available during the TEAE period, a single value $\geq 6.5\%$ will be considered and qualify the patient as NOD by default
 - For patients with several HbA1c measurements but only with the last one $\geq 6.5\%$, this single value $\geq 6.5\%$ will be considered and qualify the patient as NOD by default.
- And/or at least two fasting glucose measurements $\geq 126 \text{ mg/dL}$ (7.0 mmol/L):
 - For patients with only a single measurement available during the TEAE period, a single value ≥126 mg/dL (7.0 mmol/L) will NOT be considered and will NOT qualify the patient as NOD.
 - For patients with several fasting glucose measurements but only with the last one ≥126 mg/dL (7.0 mmol/L), this single value ≥ 126 mg/dL (7.0 mmol/L) will NOT be considered and will NOT qualify the patient as NOD.

Hepatitis C antibody

The number and percentage of patients with a post-baseline seroconversion for hepatitis C test will be provided by treatment group in post-baseline (including the TEAE and post TEAE periods). Post-baseline seroconversion is defined for patients with a negative baseline status who had either a "positive ribonucleic acid" (RNA) or a "confirmed positive antibody with negative RNA" post-baseline status as defined in the table below. Other situations require case by case evaluation and will be described individually if relevant.

The status as regards to hepatitis C virus (HCV) for a patient will be defined as follows for all evaluations (baseline and post-baseline).

	Hepatitis C Antibody (Ab) test result						
	Negative			Positive			
Reflexive test ^a – hepatitis C RNA test	Not available or HCV RNA not detected	HCV RNA detected	HCV RNA not detected ^b	HCV RNA detected	Not available		
Hepatitis C status - label	Negative	Positive RNA	Negative ^b	Positive RNA	Positive Ab – no RNA available		

Table 6 - Definition of the patient status regarding hepatitis C virus

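### The new-onset-diabetes hazard ratio is planned without baseline HbA1c; an adjusted estimate beside it would be a near-free gain in sensitivity, of a size the documents do not fix

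*SAP*

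**What the plan says.** SAP 3.1.4.1 lists, among its additional groupings of events, "New onset of diabetes (in the subgroup of patients not having diabetes at baseline". SAP 3.4.5.1 turns that list into Tier 1: "Tier 1 events will include the AESIs and grouping of adverse events as defined in Section 3.1.4.1". The stated aim for each Tier 1 event is "in order to evaluate whether the incidence is higher in the alirocumab group versus the placebo group". For the comparison of arms, "the hazard ratio (HR) will be provided together with the corresponding 95% CI", and "Hazard ratio will be calculated using a Cox model". No covariate or stratification factor follows.

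SAP 3.4.5.3 defines NOD by "combining information from adverse events, medication, and laboratory parameters". There are four routes:

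- a type 1 or type 2 diabetes TEAE;
- anti-diabetic medication started "with a confirmed diagnosis per the external diabetes experts";
- HbA1c of 6.5% or more, on at least two readings, or on a single reading if it is the only one or the last one;
- at least two fasting glucose values of 126 mg/dL or more, with a single value never sufficient.

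The same section adds: "The incidence of new onset of diabetes during the TEAE period will be analyzed in the subgroup of patients not having diabetes at baseline". It repeats the analysis within the pre-diabetes and normoglycaemic groups.

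HbA1c is taken at V1 and V3, at Month 12, yearly thereafter and at the final visit (protocol flow chart, 1.2.1). SAP 3.1.1 uses the V3 value, or V1 if V3 is missing, to classify baseline diabetes and pre-diabetes.

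**The concern.** The SAP names covariates where it wants them: region and the factor in the primary-endpoint subgroup models (3.4.4.1), region in the time-varying effect models (3.4.4.4), the baseline lipid value in the lipid analyses (3.4.7.4.1), and prognostic factors in the second step of the low-LDL-C safety analysis (3.4.5.1). The natural reading of the Tier 1 sentence is therefore a model with treatment alone. The contrast is sharpest for NOD itself. It is adjusted for prognostic factors in the non-randomized comparison within the alirocumab arm, but not in the randomized comparison.

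A patient without diabetes who starts just below 6.5% has less far to go to that threshold than one who starts at 5.3%, so baseline HbA1c should predict NOD to some degree. Leaving a prognostic covariate out of a Cox model moves the hazard ratio toward 1 relative to the covariate-conditional value and lowers the expected test statistic. For a possible harm, less sensitivity is the unwelcome direction. The sponsor treats diabetes as a live question: SAP versions 2 and 3 both changed its analysis, once on a regulator's recommendation (SAP Table 3).

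**Working it through.** **No planned figure for NOD.** The documents give no NOD event count, power or hazard ratio. As a check of the formulas only, the primary-endpoint target can be reproduced. Schoenfeld's formula with HR 0.85, one-sided 0.025 and 90% power gives 4 × (1.960 + 1.282)² / (ln 0.85)² = 42.04 / 0.02641 ≈ 1,592 events. The plan has 1,613, at which fixed-design power is 0.904. The small excess is plausibly the cost of the group-sequential design, which was not recomputed.

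**Assumed inputs, none from the documents:** 12,600 patients without diabetes (70% of 18,000), follow-up uniform on 2 to 5 years, baseline HbA1c with mean 5.75% and SD 0.35 truncated below 6.5%, two-sided 0.05.

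**Model A.** NOD hazard depends on baseline HbA1c with a given hazard ratio per SD, and the true HbA1c-conditional treatment HR is 1.15. Cox models were fitted to 2,000,000 simulated patients and standard errors rescaled to 12,600. Power = Φ(ln HR / SE − 1.96). Relative efficiency = (z unadjusted / z adjusted)².

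| Control-arm NOD | HR per SD HbA1c | Events | Unadjusted HR | Power: treatment only | + pre-diabetes yes/no | + continuous HbA1c | Relative efficiency |
|---|---|---|---|---|---|---|---|
| 5% | 1.5 | 677 | 1.150 | 0.440 | 0.443 | 0.442 | 0.995 |
| 5% | 2.5 | 677 | 1.148 | 0.431 | 0.441 | 0.442 | 0.970 |
| 5% | 4.0 | 678 | 1.143 | 0.412 | 0.427 | 0.443 | 0.915 |
| 10% | 1.5 | 1,353 | 1.149 | 0.721 | 0.727 | 0.727 | 0.986 |
| 10% | 2.5 | 1,352 | 1.143 | 0.691 | 0.713 | 0.727 | 0.920 |
| 10% | 4.0 | 1,348 | 1.134 | 0.632 | 0.668 | 0.726 | 0.806 |
| 15% | 1.5 | 2,023 | 1.148 | 0.873 | 0.879 | 0.880 | 0.976 |
| 15% | 2.5 | 2,018 | 1.139 | 0.833 | 0.859 | 0.880 | 0.871 |
| 15% | 4.0 | 2,007 | 1.125 | 0.753 | 0.802 | 0.878 | 0.716 |

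Hand check of the sixth row: SE ≈ 2/√1,348 = 0.0545. Unadjusted, ln 1.134 / 0.0545 = 2.31, so power is Φ(0.35) ≈ 0.64. Adjusted, ln 1.15 / 0.0545 = 2.56, so power is Φ(0.60) ≈ 0.73. Both agree with the table to within rounding. The gain comes from the estimate moving away from 1, not from a smaller standard error.

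A cross-check with 300 simulated trials per row showed the same pattern, with more noise. Where HbA1c was weakly prognostic, the adjusted analysis was at most 0.7 points worse, within simulation error.

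**Model B.** Events come from annual HbA1c readings (reading SD 0.2; two readings of 6.5% or more make a case) with a shift of 0.03 HbA1c points on drug. A competing non-HbA1c route, unaffected by treatment, is added at increasing rates.

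| Share through HbA1c | Overall NOD | HR: treatment only | HR: adjusted | Power: treatment only | Power: adjusted | Gain (points) |
|---|---|---|---|---|---|---|
| 100% | 4.8% | 1.177 | 1.212 | 0.517 | 0.654 | 13.7 |
| 73% | 6.5% | 1.120 | 1.136 | 0.365 | 0.444 | 7.9 |
| 48% | 9.6% | 1.064 | 1.069 | 0.190 | 0.215 | 2.5 |
| 31% | 14.2% | 1.046 | 1.047 | 0.155 | 0.162 | 0.7 |

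Limits of Model B: the non-HbA1c route is unrelated to baseline HbA1c, which understates the gain if the routes overlap. Baseline HbA1c is taken as free of reading error, which overstates it. The rule that counts a single last reading is not modelled.

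**The case against.** The case against is substantial, and most of it limits the size of the point.

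- A reader might infer that NOD is mainly HbA1c crossing 6.5%, so that baseline HbA1c must dominate. The documents do not say so. HbA1c is one of four routes and no shares are given. The single-reading rule, allowed for HbA1c and refused for glucose, tilts cases toward HbA1c but does not show that they are the majority. Model B shows how much depends on this.
- A reader might infer that the planned hazard ratio is biased toward safety. It is not. Under randomization it is a valid marginal estimate, and chance imbalance in baseline HbA1c is ordinary sampling error that the confidence interval already covers. The adjusted hazard ratio answers a conditional question.
- A reader might infer that a formal diabetes safety test loses power. Protocol 11.4.3 plans no formal inferential testing of safety data, and the SAP sets no alpha, margin or power for NOD. Power here only measures sensitivity.
- Baseline glycaemia is already used in part. NOD is analysed within the pre-diabetes and normoglycaemic groups (3.4.5.3), and HbA1c over time is summarized by arm and by baseline diabetes status (3.4.7.2), where a small mean shift may show more directly than through a yes/no event.

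The last item stands but does not close the gap. No pooled adjusted NOD hazard ratio is planned. The hazard ratios by baseline diabetes status in 3.4.5.1 belong to a different grouping, diabetes mellitus or diabetic complications. In Model A, a yes/no split at HbA1c 5.7%, which is only one of the SAP's pre-diabetes criteria, recovered part of the gain: 0.632 to 0.668, against 0.726 with continuous HbA1c.

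**Conclusion.** The point holds as one of efficiency, not of bias or type I error. The Tier 1 Cox model for NOD names no covariate, a relevant pre-treatment value is collected, and in no scenario did using it cost meaningful power.

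The size cannot be fixed from the documents. It runs from near zero, with few cases through HbA1c, weak prognostic value or low incidence, to about 12 to 14 power points, with strong prognostic value at 15% incidence or every case through HbA1c. In Model A, a conditional HR of 1.15 appears unadjusted as 1.150 to 1.125, and relative efficiency is 0.995 to 0.72. All of these figures rest on the assumed population, follow-up, HbA1c distribution and treatment effect.

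**What to change.** In SAP 3.4.5.1 or 3.4.5.3, pre-specify before unblinding a Cox model for NOD with treatment and baseline HbA1c as a continuous covariate, using V3, or V1 if V3 is missing, as in 3.1.1. State how patients with neither value are handled. Baseline fasting glucose may be added as a second covariate. Report the result beside the planned unadjusted hazard ratio, labelled as a supportive safety comparison, with a note that it is a conditional hazard ratio. Keep the planned hazard ratio, so that NOD stays comparable with the other Tier 1 events.

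The cost is a sentence or two in the SAP and one more estimate in the NOD table, from data already collected. The small downside is that two hazard ratios of different meaning stand side by side and need that note. Fixing the covariates now also avoids choosing an adjustment after the results are known, should NOD be borderline or baseline HbA1c turn out unbalanced.
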